4.5.1.6 Monitoring of Dose Administration

Vital signs (BP, heart rate, respiratory rate, and body temperature) will be obtained before investigational product administration. After investigational product administration, subjects will be monitored for immediate drug reactions; vital signs will be taken immediately, and at 10, 30, 60 minutes, and 4 and 8 hours after administration of investigational product. Discharge from the site on Day 1 will be determined by the investigator.

As with any antibody, allergic reactions to dose administration are possible. The World Health Organization has categorized anaphylaxis into 2 subgroups, which are clinically indistinguishable: immunologic (IgE-mediated and non-IgE-mediated [eg, immunoglobulin G [IgG] and immune complex mediated]) and nonimmunologic (Johansson et al, 2004). The clinical criteria for defining anaphylaxis for this study are listed in Appendix 7. A guide to the signs and symptoms and management of acute anaphylaxis is provided in Appendix 8. Appropriate drugs, such as epinephrine, antihistamines, corticosteroids, etc, and medical equipment to treat acute anaphylactic reactions must be immediately available at study sites, and study personnel should be trained to recognize and treat anaphylaxis according to local guidelines.

4.5.1.7 Reporting Product Complaints

Any defects with the investigational product must be reported *immediately* to the MedImmune Product Complaint Department by the site with further notification to the site monitor. All defects will be communicated to MedImmune and investigated further with the Product Complaint Department. During the investigation of the product complaint, all investigational product must be stored at labeled conditions unless otherwise instructed.

MedImmune contact information for reporting product complaints:

4.5.2 Additional Study Medications

No other study medications are specified for use in this clinical protocol.

4.5.3 Labeling

Labels for the investigational product will be prepared in accordance with Good Manufacturing Practice (GMP) and local regulatory guidelines. The label will fulfill GMP Annex 13 requirements for labeling. Label text will be translated into local languages, as required.

4.5.4 Storage

Store investigational product at 2°C to 8°C.

4.5.5 Treatment Compliance

Investigational product is administered by study site personnel, who will monitor compliance.

4.5.6 Accountability

The investigator's or site's designated investigational product manager is required to maintain accurate investigational product accountability records. Upon completion of the study, copies of investigational product accountability records will be returned to MedImmune. All unused investigational product will be returned to a MedImmune-authorized depot or disposed of upon authorization by MedImmune.

4.6 Treatment Assignment and Blinding

4.6.1 Methods for Assigning Treatment Groups

Subjects will be randomized in a 1:1:1:1 ratio to 1 of 4 cohorts to receive a single SC dose of 300 mg tralokinumab on Day 1 administered as either 2×1 mL injections at a flow rate of 6 mL/min for each injection (Cohort 1) or a 1×2 mL injection at flow rates of 12, 2, or 0.167 mL/min (Cohorts 2, 3, or 4, respectively). Randomization will be stratified by gender. A minimum of 5 males and 5 females will be randomized to each cohort; the additional subjects may be of either sex. The allocation to each cohort will be open label. Only the injection-site assessor will be blinded to treatment allocation of all subjects (except those randomized to Cohort 1 due to the requirement for 2 separate injections).

The procedure for randomization will be as follows:

- 1. On Day 1, the investigator or designee will confirm subject eligibility.
- 2. The SID number and gender will be communicated to the pharmacist/designee.
- 3. The pharmacist/designee will use a randomization list to assign a randomization number and dispense the investigational product to the subject.
- 4. The site team will record the appropriate information in the subject's medical records. The pharmacist/designee will maintain a master investigational product accountability log and batch preparation records.

Investigational product (tralokinumab) must be administered the same day the investigational product is assigned. If there is a delay in the administration of investigational product such that it will not be administered within the specified timeframe, the study monitor must be notified immediately.

4.6.2 Methods for Ensuring Blinding

Both site and sponsor personnel will be unblinded, with the exception of a blinded injection-site assessor who will evaluate local reactions to investigational product administration. The blinded injection-site assessor will be unaware of the treatment allocation

of all subjects where practicably possible (eg, for subjects randomized to Cohort 1, the requirement for 2 separate injections makes blinding to treatment allocation impossible) and will not observe the preparation or administration of investigational product or participate in the conduct of the study outside of the injection-site assessments (see Section 4.3.3.4).

4.7 Restrictions During the Study and Concomitant Treatment(s)

The investigator must be informed as soon as possible about any medication taken from the time of screening until the end of the clinical phase of the study (final study visit). Any concomitant medication(s), including over-the-counter, herbal, and vitamin preparations, taken during the study will be recorded in the eCRF.

4.7.1 Permitted Concomitant Medications

Investigators may prescribe concomitant medications or treatments deemed necessary to provide adequate supportive care or to treat AEs as deemed necessary, except for those medications identified as "excluded" as listed in Section 4.7.2. Specifically, subjects should receive full supportive care during the study and treatment with antibiotics, anti-emetics, anti-diarrheals, and analgesics, and other care as deemed appropriate, and in accordance with their institutional guidelines. All concomitant medications used by the subject from screening through Day 57 will be recorded.

4.7.2 Prohibited Concomitant Medications

The use of regular concomitant medications during the study (except those described in Sections 4.5.2), including over-the-counter medications, herbal supplements, and vitamins is discouraged and should be discussed in advance with the sponsor's medical monitor.

The following medications are considered exclusionary and are not permitted during the study. The sponsor must be notified if a subject receives any of these medications during the study:

- 1. Immunosuppressive medication (eg, methotrexate, troleandomycin, oral gold, cyclosporine, azathioprine, oral corticosteroid dose > 10 mg/day prednisone [or equivalent], intramuscular long-acting depot corticosteroid)
- 2. Oral corticosteroid burst or short-acting systemic corticosteroid; except for the treatment of any allergic reaction, including anaphylaxis
- 3. Investigational agents
- 4. Marketed biologics, including omalizumab
- 5. Immunoglobulin or blood products
- 6. Use of any oral or ophthalmic ~-adrenergic antagonist (eg, propranolol)

7. Live attenuated vaccines

4.8 Statistical Evaluation

4.8.1 General Considerations

Data will be provided in data listings sorted by SID number. Categorical data will be summarized by the number and percentage of subjects in each category. Continuous variables will be summarized by descriptive statistics, including mean, standard deviation, median, minimum, and maximum. Details of endpoint analyses will be described in the statistical analysis plan (SAP).

Analysis Populations

The PK population is defined as all subjects in the as-treated population with at least one detectable tralokinumab serum concentration and for whom the PK parameters can be adequately estimated.

The as-treated population includes all subjects who receive any amount of investigational product. Subjects will be included in the as-treated population according to the injection flow rate received, even if different from that to which the subject was randomized. Demographics, safety and tolerability endpoints, and biomarkers will be summarized based on the as-treated population.

4.8.2 Sample Size and Power Calculations

The number of subjects planned for this study is based on the number required to obtain adequate PK data while exposing as few healthy volunteer subjects as possible to tralokinumab and procedures. A total of 15 subjects per treatment arm is considered sufficient to detect an approximately 1.5-fold difference in PK parameters between cohorts and will provide exploratory information regarding local tolerability.

A previous single-dose study investigating the PK of tralokinumab (Study CD-RI-CAT-354-1054) showed a coefficient of variation (CV) of 37% for area under the serum concentration-time curve from zero to infinity (AUCO-). Assuming the same CV across the cohorts and using a two-sided two-sample t-test at a significance level of 0.05, with 15 subjects per cohort the study will be 84% powered to detect a 1.5-fold difference in AUC_{0-} between Cohort 1 and any of the other treatment cohorts.

4.8.3 Pharmacokinetics

The primary endpoint for this study is PK parameters. Using the serum concentrations of tralokinumab, the PK of tralokinumab will be analyzed using the noncompartmental method as implemented in Phoenix WinNonlin® version 6.3 or higher.

The following PK parameters will be estimated by noncompartmental analysis: $AUC_{(0-\sim)}$; AUC to last observation (AUC_{0-t}); C_{max}; time to C_{max} (T_{max}); terminal-phase half-life (t_{1/2}); apparent systemic clearance (CL/F); apparent terminal-phase volume of distribution (Vz/F).

Descriptive statistics for serum tralokinumab concentration data for the PK population will be provided by cohort and will include N, arithmetic mean, standard deviation (SD), percent CV, median, minimum, and maximum.

4.8.4 Safety and Tolerability

4.8.4.1 Analysis of Investigational Product Fluid Leakage

The degree of injection site leakage following injections of 300 mg tralokinumab will be recorded and summarized by cohort; no statistical analysis will be applied.

4.8.4.2 Analysis of Injection-site Pain Intensity

Visual analogue scale values for injection site pain intensity will be summarized for each cohort at each time point using descriptive statistics. The distribution of the pain intensity scores will be examined and the between-cohort difference will be explored.

4.8.4.3 Analysis of Injection-site Pruritus

Visual analogue scale values for injection site pruritus will be summarized for each cohort at each time point using descriptive statistics. The distribution of the pruritus scores will be examined and the between-cohort difference will be explored.

4.8.4.4 Analysis of Local Injection-site Reactions

Local injection site reactions will be recorded on a specific questionnaire (Appendix 2) by the blinded assessor and will be summarized by descriptive statistics by cohort over time.

4.8.4.5 Analysis of Overall Safety Profile

The safety profile of tralokinumab will be assessed at completion of the study primarily by summarizing TEAEs including treatment-emergent serious adverse events (TESAEs). All TEAEs, including TESAEs, will be summarized by system organ class and preferred term,

by severity, and by relationship to the investigational product. The occurrence of TEAEs to tralokinumab will be collected and summarized from the start of the tralokinumab injection on Day 1 through the end of study (Day 57). No formal statistical analysis will be applied.

Laboratory measurements as well as their changes from baseline at each collection time point and shift from baseline, if applicable, will be summarized descriptively. Significant vital sign measurements and physical examination findings will also be summarized using descriptive analyses. No formal statistical analysis will be applied.

4.8.5 Analysis of Immunogenicity

The immunogenicity of tralokinumab will be evaluated. The number and percentage of subjects with confirmed positive serum antibodies to tralokinumab will be reported by cohort. If possible, the incidence of ADA positivity will be correlated with the observed PK.

4.8.6 Analysis of Serum Biomarkers

Serum biomarkers (including periostin and DPP-4) will be summarized by descriptive statistics by cohort. This analysis will be presented separately by the sponsor.

4.8.7 Interim Analysis

No interim analyses are planned.

5 ASSESSMENT OF SAFETY

5.1 Definition of Adverse Events

The International Conference on Harmonisation (ICH) Guideline for Good Clinical Practice (GCP) E6(R1) defines an AE as:

• Any untoward medical occurrence in a patient or clinical investigation subject administered a pharmaceutical product and which does not necessarily have a causal relationship with this treatment. An AE can therefore be any unfavorable and unintended sign (including an abnormal laboratory finding), symptom, or disease temporally associated with the use of a medicinal product, whether or not considered related to the medicinal product.

An AE includes but is not limited to any clinically significant worsening of a subject's pre-existing condition. An abnormal laboratory finding (including ECG finding) that requires medical intervention by the investigator, or a finding judged by the investigator as medically significant should be reported as an AE. If clinical sequelae are associated with a laboratory abnormality, the diagnosis or medical condition should be reported (eg, renal failure,

hematuria), not the laboratory abnormality (eg, elevated creatinine, urine red blood cell increased). Abnormal laboratory values that are not, in the investigator's opinion, medically significant and do not require intervention should not be reported as AEs.

Adverse events may be treatment emergent (ie, occurring after initial receipt of investigational product) or nontreatment emergent. A nontreatment-emergent AE is any new sign or symptom, disease, or other untoward medical event that begins after written informed consent has been obtained but before the subject has received investigational product.

Elective treatment or surgery or preplanned treatment or surgery (that was scheduled prior to the subject being enrolled into the study) for a documented pre-existing condition that did not worsen from baseline is not considered an AE (serious or nonserious). An untoward medical event occurring during the prescheduled elective procedure or routinely scheduled treatment should be recorded as an AE or SAE.

5.2 Definition of Serious Adverse Events

An SAE is any AE that:

- Results in death
- Is immediately life-threatening
- Requires inpatient hospitalization or prolongation of existing hospitalization
- Results in persistent or significant disability/incapacity
- Is a congenital anomaly/birth defect in offspring of the subject
- Is an important medical event that may jeopardize the subject or may require medical intervention to prevent one of the outcomes listed above

Medical or scientific judgment should be exercised in deciding whether expedited reporting is appropriate in this situation. Examples of medically important events are intensive treatment in an emergency room or at home for allergic bronchospasm, blood dyscrasias, or convulsions that do not result in hospitalizations; or development of drug dependency or drug abuse.

5.3 Definition of Adverse Events of Special Interest

An adverse event of special interest (AESI) is one of scientific and medical interest specific to understanding of the investigational product and may require close monitoring and rapid communication by the investigator to the sponsor. An AESI may be serious or nonserious. The rapid reporting of AESIs allows ongoing surveillance of these events in order to characterize and understand them in association with the use of this investigational product.

Hepatic function abnormality meeting the definition of Hy's law is considered an AESI. See Section 5.6.2 for the definition and reporting of AESIs of hepatic function abnormality.

5.4 Recording of Adverse Events

Adverse events will be recorded on the eCRF using a recognized medical term or diagnosis that accurately reflects the event. Adverse events will be assessed by the investigator for severity, relationship to the investigational product, possible etiologies, and whether the event meets criteria of an SAE and therefore requires immediate notification to MedImmune Patient Safety. See Section 5.2 for the definition of SAEs and Appendix 6 for guidelines for assessment of severity and relationship. If an AE evolves into a condition that meets the regulatory definition of "serious," it will be reported on the SAE Report Form.

5.4.1 Local Injection-site Reactions

Local injection site reactions are of specific interest and will be recorded in detail on dedicated and standardized injection site assessment questionnaire (Appendix 2) at each time point post investigational product administration. In the case of injection-site rashes, reference should be made to the definitions of rash morphology descriptors found in Appendix 3. As a result of this targeted assessment, local injection-site reactions will not require reporting as AEs on the AE eCRF unless they meet one or more of the following criteria:

- Fulfils the criteria for an SAE
- Leads to premature termination of the injection during investigational product administration
- Requires concomitant medication or other medically important intervention
- Has an impact on the general condition of the subject as judged by the investigator

Where it may help with assessment and interpretation of individual injection-site reactions, anonymized photographs of such reactions may be taken and stored with the source documents. Subjects will be asked to provide specific consent to allow photographs to be taken for this purpose as part of the main consent form.

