3.2.3 Rationale for Endpoints

Primary Endpoint

The primary endpoint of the study is the PK of tralokinumab. Each subject will receive a single dose of 300 mg tralokinumab by one of 4 administration regimens and 57 days of follow up. Based on prior data, the maximum concentration $_{(Cmax)}$ of tralokinumab usually occurs between 2-9 days with a half-life of approximately 21 days following SC administration. Therefore, the sampling scheme will provide adequate samples for the characterization of $_{Cmax}$ and area under the serum concentration-time curve (AUC) parameters through noncompartmental analysis. The PK parameters associated with a single 2 mL injection of tralokinumab at different flow rates will be compared to those associated with 2×1 mL injections of tralokinumab to determine the feasibility of larger volume delivery and to provide information to aid in the design of the final device.

Secondary Endpoints

Injection site pain will be measured using a 100 mm visual analogue scale (VAS; see Appendix 4). Local injection-site tolerability parameters will also be measured, including injection-site itch and visual assessment of the injection site for reactions such as erythema, rash, etc. As local injection-site reactions are of specific interest, they will be recorded in detail on a dedicated and standardized injection-site questionnaire (Appendix 2) at each time point post-injection. These targeted assessment events will not require reporting as adverse events (AEs) on the AE electronic case report form (eCRF), unless they meet one or more of the following criteria:

- Fulfils the criteria for a serious adverse event (SAE)
- Leads to premature termination of the injection during investigational product administration
- Requires concomitant medication or other medically important intervention
- Has an impact on the general condition of the subject as judged by the investigator

These data will be used to determine the overall tolerability of a single 2 mL injection of tralokinumab at different flow rates to determine the feasibility of this approach compared to 2×1 mL injections and to provide information to aid in the design of the final delivery device.

The degree of fluid leakage from the injection site will be assessed immediately following all injections to determine if the flow rates affect delivery of the 2 mL injection volume.

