4.2.3 Follow-up Period

Table 4.2.3-1 shows all procedures to be conducted during the follow-up period.

Whenever vital signs and blood draws are scheduled for the same nominal time, the assessments should occur in the following order: vital signs, then blood draws. For assessment of injection-site reactions, these should be done in the order specified in the table.

Study Period					Follow-up				
Visit Number	V3	V4	V5	V6	V7	V8	V9	V10	V11
Procedure / Study Day or Week	Day 2	Day 4	Day 6	Day 8	Day 10 (~ 1 d)	Day 15 (~ 1 d)	Day 22 (~ 2 d)	Day 36 (~ 2 d)	Day 57 (~ 2 d)
Physical examination									X
Weight									X
Assessment of AEs/SAEs	Х	X	X	X	X	Х	X	X	X
Concomitant medications	Х	X	X	X	X	Х	X	X	X
Vital signs									X
Blood collection for:									
Serum chemistry and hematology				X		X		X	X
PK blood sample	X ^a	X	X	Х	X	X	X	X	X
IM blood sample									X
Serum biomarkers				X				X	X
Urine collection for:									
Urinalysis									X
Assessment of injection site for:									
Pain intensity via VAS	X ^b	X ^{c, d}							
Pruritus via VAS	X ^b	X ^{c, d}							
Local injection site reactions	X ^b	X ^{c, d}							

Table 4.2.3-1Schedule of Follow-up Procedures

AE = adverse event; d = day; IM = immunogenicity; PK = pharmacokinetic; SAE = serious adverse event; V = visit; VAS = visual analogue scale.

^a PK sample to be collected at 24 hours (~ 30 minutes) relative to administration time on Day 1

^b For each subject, measurements to be taken at 24 hours (Day 2; ~ 1 hour) relative to administration time

^c For each subject, measurements to be taken at 72 hours (~ 1 hour) relative to administration time

^d Symptoms and/or signs at the injection site persisting beyond 72 hours will be followed through resolution

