4.3.3.4 Local Injection-site Reactions

Local injection site reactions will be assessed by a blinded assessor (see Section 4.6.2) immediately post-injection, once the needle insertion set has been withdrawn (after the second injection in Cohort 1), and at 10, 20, 30, and 60 minutes (~ 3 minutes), and then at 2, 4, and 8 hours (~ 10 minutes), and 24 and 72 hours (\pm 1 hour) post-injection for all 4 cohorts as outlined in Table 4.2.2-1, Table 4.2.2-2, and Table 4.2.3-1.

The blinded assessor will assess the injection site at each time point post-injection for the presence or absence of signs and/or symptoms of local injection site reaction, including erythema, hematoma or bleeding, local warmth, swelling, and/or rash. In the case of

injection-site rashes, reference should be made to the definitions of rash morphology descriptors found in Appendix 3.

For subjects in Cohort 1 who will receive 2×1 mL injections of tralokinumab, an overall assessment of both injection sites should be recorded at each time point post-injection. Where there are differences in injection site reactions between the two sites for a particular subject, the most severe reaction should always be recorded.

As local injection-site reactions are of specific interest, they will be recorded in detail on a dedicated and standardized injection site assessment questionnaire (Appendix 2) at each time point post-injection. These targeted assessment events will not require reporting as AEs on the AE eCRF, unless they meet 1 or more of the following criteria:

- Fulfils the criteria for an SAE
- Leads to premature termination of the injection during investigational product administration
- Requires concomitant medication or other medically important intervention
- Has an impact on the general condition of the subject as judged by the investigator

Any injection-site reactions that are ongoing beyond 72 hours will be followed up to resolution and the signs/symptoms will be recorded on a local injection-site assessment questionnaire (Appendix 2) at each subsequent visit.

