- 4. Inject the investigational product into the SC tissue using the syringe pump at the flow rates specified for each cohort.
- 5. Keep the needle in place for **10 seconds** after the syringe pump has stopped delivering investigational product and prior to needle withdrawal.
- 6. *Do not* massage the injection site following the injection.
- 7. Some investigational product may remain in the syringe, extension set, and infusion set after the infusion is completed.
- 8. All injection-site assessments are to start after needle has been withdrawn.

If any of the following should occur, the investigator should reschedule the visit and investigational product should not be administered:

- The subject has an intercurrent illness that in the opinion of the investigator and/or medical monitor may compromise the safety of the subject in the study (eg, viral illnesses)
- The subject is febrile (≥ 38°C; ≥ 100.4°F) within 72 hours prior to investigational product administration

Injection site(s) will be assessed immediately post-injection, once the needle insertion set has been withdrawn, and at 10, 20, 30, and 60 minutes and then at 2, 4, 8, 24, and 72 hours post-injection as described in Section 4.3.3. For Cohort 1, assessments will be done after the second injection has been administered. At each time point the blinded assessor will complete the injection site assessment questionnaire; but will not complete an AE eCRF for injection-site reactions, unless the reaction meets one of the following criteria:

- Fulfils the criteria for an SAE
- Leads to premature termination of the injection during investigational product administration
- Requires concomitant medication or other medically important intervention
- Has an impact on the general condition of the subject as judged by the investigator

Injection-site reactions persisting beyond 72 hours will be followed up to resolution.

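### The AE exemption for local injection-site reactions has no time limit, but after 72 hours the questionnaire that justifies it takes only reactions already under way

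*Protocol*

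**What the plan says.** Section 5.4.1 gives the targeted questionnaire (Appendix 2) as the reason for the exemption: "As a result of this targeted assessment, local injection-site reactions will not require reporting as AEs on the AE eCRF". The exceptions are a reaction that is serious, that ends the injection early, that needs medication or another important intervention, or that affects the subject's general condition in the investigator's judgement. No period is stated.

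The questionnaire itself has a fixed timetable. Section 4.3.3.4 sets checks immediately after the injection, at 10, 20, 30 and 60 minutes, "and then at 2, 4, and 8 hours (~ 10 minutes), and 24 and 72 hours". After that it provides only that "Any injection-site reactions that are ongoing beyond 72 hours will be followed up to resolution", with the form completed at each later visit. Footnote d of Table 4.2.3-1 agrees: "Symptoms and/or signs at the injection site persisting beyond 72 hours will be followed through resolution". In that table the injection-site rows are marked at Visits 3 and 4 (Days 2 and 4) and are blank from Visit 5 to Visit 11.

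The exemption is repeated in Section 3.2.3, Table 4.2.2-1 footnote f and Section 4.3.3.4 in different terms: "These targeted assessment events will not require reporting as AEs on the AE eCRF". In Section 4.5.1.5 it is an instruction to the blinded assessor, who fills in the questionnaire at each time point "but will not complete an AE eCRF for injection-site reactions, unless the reaction meets one of the following criteria".

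Section 5.4.2 collects AEs from consent to Day 57, and Table 4.2.3-1 schedules an AE assessment at every follow-up visit.

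**The concern.** The reason for the exemption is that the questionnaire already holds the event. For a reaction that begins after 72 hours that reason no longer applies, because nothing in the protocol opens a questionnaire for it. The exemption in Section 5.4.1 nevertheless continues to cover local reactions as a class.

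Local tolerability is part of the first secondary objective (Section 2.1.2). Post-injection reactions are a secondary endpoint with no 72-hour limit (Section 2.2.2), and Section 3.2.3 says the data will help judge whether a single 2 mL injection is feasible. The reaction summaries come from the questionnaire (Section 4.8.4.4) and the TEAE summaries from AE records (Section 4.8.4.5). An event entered on neither form is in neither summary, and its absence cannot be told apart from a reaction that did not occur.

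**Working it through.** The protocol gives no figure for late reactions. Its one design calculation, the power for AUC in Section 4.8.2, does not enter this point. The check is therefore a comparison of texts, with simple arithmetic on the schedule.

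**Step 1: follow one case through the rules.** Suppose a subject's site is clear at 72 hours and the subject reports a new, untreated, non-serious local rash at the Day 8 visit, with no effect on general condition.

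- Scheduled questionnaire: none. The last is at 72 hours (Section 4.3.3.4; Table 4.2.3-1, Visit 4).
- Continued questionnaire: does not apply. Section 4.3.3.4, Section 4.5.1.5 and Table 4.2.3-1 footnote d cover only reactions already present at 72 hours.
- AE form under Section 5.4.1 read literally: not required, because the event is a local injection-site reaction and meets none of the four exceptions.
- AE form under the wording of Sections 3.2.3 and 4.3.3.4 and Table 4.2.2-1 footnote f: arguably required. The rash was never an event of the targeted assessment, so Section 5.4.2 would apply.

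The same rash is thus either not required on any form or required as an AE, depending on which section the site staff follow.

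**Step 2: how much of follow-up has scheduled site checks.**

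- Post-dose follow-up: Day 57 − Day 1 = 56 days.
- Period with scheduled site checks: 72 h ÷ 24 = 3 days.
- Remainder: 56 − 3 = 53 days, and 53 ÷ 56 = 94.6%.
- Visits in the remainder: Days 6, 8, 10, 15, 22, 36 and 57, which is seven. Each has an AE assessment and none has a scheduled site check for new reactions.

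The 94.6% is the share of follow-up without a scheduled site check. It is not a share of events lost.

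**Step 3: can the number of events be estimated?** No. The protocol gives no rate of reactions with onset after 72 hours, and no figure for how many would meet an exception or be recorded anyway.

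**The case against.** The strongest reply is that the exemption is tied to its cause. Section 5.4.1 opens by pointing to the targeted assessment, and three of the four repeats limit it to events of that assessment. On that reading a reaction first seen on Day 8 is an ordinary AE under Section 5.4.2, and AEs are assessed at each of the seven later visits. Section 4.5.1.5 addresses only the blinded assessor at the scheduled times and does not lift the investigator's general duty. Reactions meeting any of the four exceptions are AEs whenever they occur. The Day 57 physical examination includes the skin, and clinically significant findings are recorded.

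All of this stands and narrows the point. It does not close it: Section 5.4.1 is the section that governs AE recording of these reactions, its exemption covers them as a class, and nothing in the text says which reading prevails.

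Four stronger inferences might tempt a reader, and the protocol does not support them.

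- *Late reactions are recorded nowhere.* The wording lifts a duty; it does not forbid recording, and the exceptions still apply.
- *Reactions that start and clear between two checks within 72 hours are lost for the same reason.* In that period the exemption and the questionnaire run together, so the mismatch does not arise. Section 4.3.3.4 does describe each check as presence or absence: "The blinded assessor will assess the injection site at each time point post-injection for the presence or absence of signs and/or symptoms". But the content of the Appendix 2 form is not in the text available here, so whether it asks about the interval since the last check cannot be verified.
- *Late reactions are to be expected because peak exposure comes late.* Section 3.2.3 says that the maximum concentration "usually occurs between 2-9 days with a half-life of approximately 21 days following SC administration". That is a serum figure, and no section links local reactions to it. Section 1.5 relates injection-site tolerability to volume, tissue pressure and flow rate.
- *A definite number of events would be lost.* Any such number needs an assumed rate for which the protocol offers no basis.

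**Conclusion.** The point holds as a conflict of scope. Under the literal reading of Section 5.4.1, a local reaction that first appears after 72 hours and meets none of the four exceptions is required on neither the questionnaire nor the AE form. Under the narrower reading it is an AE. Because both readings are open, recording may differ between subjects, and some late reactions could be absent from both the reaction and the TEAE tables.

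The exposed period is 53 of 56 post-dose days, tempered by seven visits with an AE assessment. The events at risk are limited to untreated, non-serious reactions with no effect on general condition; their number is unknown. The conclusion rests on the wording of the sections cited and assumes nothing about how often late reactions occur. No sample size, power or significance level is affected. The change is worth making before enrolment, since events left unrecorded cannot be reliably recovered afterwards.

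**What to change.** Limit the exemption in Section 5.4.1 to reactions actually recorded on an Appendix 2 questionnaire, and align Section 3.2.3, Table 4.2.2-1 footnote f, Section 4.3.3.4 and Section 4.5.1.5 with it. Add one sentence stating that any local injection-site reaction with onset after 72 hours is recorded either as an AE or on an unscheduled Appendix 2 form. Choose one route and apply it to every subject. If the unscheduled form is chosen, include these reactions in the summaries of Section 4.8.4.4.

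The AE enquiry already made at each follow-up visit is enough to find these events, so no visit or procedure is added. The cost is a wording change in five places and, if that route is taken, an unscheduled copy of an existing form. If late reactions are entered as AEs, the TEAE count may rise slightly.
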